5.7.3. Subgroup Efficacy Analysis

Subgroup efficacy analyses will be performed based on the following factors, respectively:

- Age group (<65, ≥ 65 - < 75 , ≥ 75)
- Race
- Geographical region
- Number of prior systemic therapies
- ECOG (0, 1)
- Prior radiotherapy (Yes, No)

5.8. Analysis of Safety Data

The analysis of safety and tolerance will be performed on the FAS, as defined in Section 3.1 .

5.8.1. Adverse Events

Summaries that include frequencies and proportions of patients reporting AEs will include the PTs and the SOCs.

Summaries of TEAEs will include: TEAEs, Treatment related TEAEs, Serious TEAEs, Treatment-related Serious TEAEs, treatment-emergent AESI, and imAEs. For TEAEs, the following will be summarized:

- The number and proportions of patients reporting at least 1 TEAE, presented by SOC and PT
- TEAEs by severity (NCI-CTCAE, version 5.0), presented by SOC and PT
- TEAEs related to treatment, presented by SOC and PT
- SAEs, presented by SOC, PT and NCI-CTCAE grade
- TEAEs leading to permanent treatment discontinuation, presented by SOC, PT and NCI-CTCAE grade
- TEAEs leading to death, presented by SOC and PT
- IRRs by SOC, PT and NCI-CTCAE grade
- Injection site reaction by SOC, PT, and NCI-CTCAE grade
- AESIs by SOC, PT and NCI-CTCAE grade
- Treatment-emergent imAEs by SOC, PT and NCI-CTCAE grade

For each TEAE summary presented by SOC and PT, the summary table will be sorted by decreasing frequency of SOC and PT. For TEAE summary presented by PT, the summary table will be sorted by decreasing frequency of PT.

5.8.2. Clinical Laboratory Measurements

Laboratory test results will be summarized by baseline and change from baseline to each visit with descriptive statistics.

Summary tables for worst laboratory values during on-treatment period with NCI CTCAE all grade and grade ≥ 3 will be generated. Shift tables from baseline to worst post-treatment NCI CTCAE grade during on-treatment period will be generated.

5.8.3. Analysis of Vital Signs

Vital signs (pulse, sitting blood pressures, and temperature) will be summarized by Baseline and change from Baseline to each scheduled assessment time with descriptive statistics.

5.8.4. Analysis of 12-Lead ECG

ECG parameters will be summarized by Baseline and change from Baseline to each scheduled assessment time with descriptive statistics.

ECG status (ie, normal, abnormal, not clinically significant, and abnormal clinically significant) will be reported. Shift tables from baseline to worst post-baseline findings (normal, abnormal not clinically significant, and abnormal clinically significant) during on-treatment period will be generated.

5.9. Analysis of Pharmacokinetic and Antibody Data

5.9.1. Analysis of Pharmacokinetic Data

The concentrations of total cemiplimab will be assessed at multiple time points throughout the study treatment and summarized by descriptive statistics and listed by patient, timepoint, and dose.

5.9.2. Analysis of Anti-Drug Antibody Data

The immunogenicity variables described in Section 4.6.2 will be summarized using descriptive statistics. Immunogenicity for cemiplimab will be characterized by the ADA response observed:

- ADA Negative, defined as ADA negative response in the REGN2810 ADA assay at all time points, regardless of any missing samples.
- Pre-existing immunoreactivity, defined as a positive response in the cemiplimab ADA assay at baseline, with all post-dose ADA results negative, or a positive assay response at baseline, with all post-dose ADA assay responses less than 9-fold over baseline titer levels
- Treatment-emergent ADA response, defined as any post-dose positive response in the cemiplimab ADA assay when the baseline results are negative
 - Treatment-emergent ADA response may be further characterized as persistent, transient, or indeterminate.
 - Persistent Response – Treatment-emergent ADA positive response with two or more consecutive ADA positive sampling time points, separated by at least 16-week period (based on nominal sampling time), with no ADA negative samples in between, regardless of any missing samples.
 - Indeterminate Response – Treatment-emergent ADA positive response with only the last collected sample positive in the ADA assay, regardless of any missing samples.
 - Transient Response – Treatment-emergent ADA positive response that is not considered persistent or indeterminate, regardless of any missing samples.
- Treatment boosted ADA response, defined as any post-dose positive response in cemiplimab ADA assay that is 9-fold over baseline titer levels when baseline is positive in the ADA assay
- Maximum ADA Titer values
 - Low (titer <1,000)
 - Moderate (1,000? titer \leq 10,000)
 - High (titer >10,000)

Listings of pre-existing, treatment-boosted, and treatment-emergent ADA responses, ADA titers positivity presented by patient and time point will be provided. Incidence of treatment-emergent

ADA will be assessed as absolute occurrence (N) and percent of patients (%), grouped by study cohorts and ADA titer level.

5.10. Association of Immunogenicity with Exposure, Safety and Efficacy

5.10.1. Immunogenicity and Exposure

Potential association between immunogenicity and systemic exposure to cemiplimab will be explored. Plots of individual cemiplimab concentration time profiles may be provided to examine the potential impact of ADA category and maximum titer category on these profiles.

5.10.2. Immunogenicity and Safety and Efficacy

Potential association between immunogenicity variables and safety may be explored with a primary focus on the following safety events during the TEAE period:

- Infusion reactions
- Hypersensitivity (SMQ: Hypersensitivity [Narrow])
- Anaphylaxis (SMQ: Anaphylactic Reaction [Narrow])

Potential association between immunogenicity variables and efficacy endpoints may be explored (e.g., scatter plot or spaghetti plot).

The safety and efficacy analyses mentioned above will be conducted using the following categories:

- ADA Positive
 - Treatment-emergent
 - Treatment-boosted
- Maximum post-baseline titer category in ADA positive patients

5.11. Analysis of Exploratory Biomarker Data

The association of PD-L1 expression in tumor and infiltrating immune cells with clinical efficacy and available data on changes in HPV antigen specific T cell responses in a subset of patients will be included in the CSR. Analysis of all other exploratory pharmacodynamic and baseline predictive biomarker data will be included in a separate biomarker analysis report.

6. DATA CONVENTIONS

The following analysis conventions will be used in the statistical analysis.

6.1. Definition of Baseline for Efficacy/Safety Variables

Unless otherwise specified, the Baseline assessment for all measurements will be the latest available valid measurement taken prior to the administration of investigational product.

6.2. Data Handling Convention for Efficacy Variables

Patients who are deemed NE according to RECIST version 1.1. will be considered as not reaching PR/CR in calculating ORR, i.e. they are not considered as responders in the numerator of ORR, but they are counted in the denominator of ORR.

6.3. Definition of Study Day

Study day 1 is the day of patient receiving first dose of study drug. Study day –1 is the day before patient receiving first dose of study drug. There is no Day 0.

For events prior to the first day a patient receiving study drug, the study day is defined as date of the date of event - first dose of study drug; for events on or after the first dose of study drug, the study day is defined as date of event - date of the first dose of study drug +1.

6.4. Data Handling Convention for Missing Data

No missing data imputation is planned in this study unless specified otherwise.

For categorical variables, patients with missing data are not included in calculations of percentages unless otherwise specified. When relevant, the number of patients with missing data is presented.

Medication missing/partial dates

To determine whether a medication is prior, concomitant or post-treatment medication, the missing medication start date is estimated as early as possible up to date of the first study treatment, and the missing medication end date is estimated as late as possible. If the medication start date is missing, the onset day will not be imputed in medication listings.

Date of first / last study treatment

Date of first injection or infusion is the first non-missing start date of dosing filled in the CRF “Investigational Product” module.

If a patient’s date of the last dose is totally missing or unknown, his/her last visit date will be substituted.

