4.3. Pre-Treatment / Concomitant Medication

Medications/Procedures will be recorded from the day of informed consent until 90 days after the last study treatment or 1 day prior to starting a new treatment for cervical cancer, whichever is first. Medications will be coded to the ATC level 2 (therapeutic main group) and ATC level 4 (chemical/therapeutic subgroup), according to the latest available version of WHO Drug Dictionary (WHODD). Patients will be counted once in all ATC categories linked to the medication.

Prior cancer related medications/procedures: medications taken, or procedures performed prior to administration of the study drug, particularly, prior cancer related surgery, prior cancer related radiotherapy, and prior cancer related systemic therapy will be summarized.

Pre-treatment medications/procedures: non-study medications for which administration started and discontinued before a patient received the first dose of study drug.

Concomitant medications/procedures: any treatment administered from the time of informed consent until 90 days after the last study treatment or start of another systemic anticancer therapy, whichever comes first, will be considered concomitant treatment. This includes medications and other therapies for which administration started 30 days before the first dose of the study and will continue during the study, as well as any therapies started in the follow-up period to treat a study-drug-related AE.

Post treatment anti-cancer medications/procedures: anti-cancer medications and other anti-cancer therapies that started after discontinuation of the study drug.

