4.4.2. Secondary Efficacy Variables

Duration of response (DOR) is determined for patients with BOR of CR or PR. DOR is measured from the time measurement criteria are first met for CR/PR (whichever is first recorded) until the first date of recurrent or progressive disease (radiographic), or death due to any cause.

- Patients who do not have a documented tumor progression or death will be censored at the last evaluable tumor assessment.
- Patients who do not have a documented tumor progression or death before initiation of new anti-cancer therapy will be censored at the last evaluable tumor assessment prior to or on the date of new anti-cancer therapy.

Progression-free survival (PFS) is measured from the start of treatment until the first date of recurrent or progressive disease (radiographic), or death due to any cause.

- Patients who do not have a documented tumor progression or death will be censored at the last evaluable tumor assessment.

- Patients who do not have a documented tumor progression or death before initiation of new anti-cancer therapy will be censored at the last evaluable tumor assessment prior to or on the date of new anti-cancer therapy.
- Patients who do not have any evaluable post-baseline tumor assessment and do not die will be censored on the date of first study treatment.

Overall survival (OS) is measured from the start of treatment until death due to any cause. Patients who do not die will be censored at the last date that patient is documented to be alive. As many patients may receive new anti-cancer therapy after disease progression, a sensitivity analysis of OS will be conducted by censoring patients at the first date of a new anti-cancer therapy is taken.

Time to tumor response (TTR) is determined for patients with BOR of CR or PR. TTR is measured from the start of treatment until the time measurement criteria are first met for CR/PR (whichever is first recorded).

For all the above time-to-event variables, the time to event (day) is the date of event/censor - the date of first study treatment + 1.

Disease control rate (DCR) is determined by the portion of patients with BOR of CR, PR, or SD.

Durable disease control rate (dDCR) is defined as the proportion of patients best overall response of CR, PR, or SD without progression for at least 12 weeks.

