4.5. Safety Variables

Patient safety will be assessed through the collection of reported adverse events (AEs), clinical laboratory data, vital signs, ECG, and physical exam.

Period of observation: The observation period will be divided into three segments: pretreatment, on-treatment, and posttreatment.

- The pretreatment period is defined as the time from signing the ICF to before the first dose of study drug.
- The on-treatment period is defined as the day from first dose of study drug to the last dose of study drug plus 90 days, or 1 day prior to starting a new treatment for cervical cancer, whichever is first.
 - The period from the first dose of ISA 101b to the first dose of cemiplimab reflects the on-treatment period associated with ISA 101b alone.
- The posttreatment period is defined as the day after the on-treatment period until 1 year after the end of the on-treatment period or the start of a new treatment for cervical cancer, whichever is first.

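### Under SAP 6.4 an anti-cancer therapy with no start date can never be classed as post-treatment, and no rule covers an incomplete new-therapy date elsewhere

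*SAP*

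**What the plan says.** SAP 6.4 gives its medication-date rule a stated purpose: "To determine whether a medication is prior, concomitant or post-treatment medication". For that purpose, "the missing medication start date is estimated as early as possible up to date of the first study treatment"; an unknown stop date goes to the latest day it could be. The same section sets a general default, "No missing data imputation is planned in this study unless specified otherwise", and adds: "If the medication start date is missing, the onset day will not be imputed in medication listings". It makes no exception for therapy that the site has recorded as subsequent to study treatment.

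The only post-treatment category in SAP 4.3 is "anti-cancer medications and other anti-cancer therapies that started after discontinuation of the study drug".

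The start date of new anti-cancer therapy is used in three other places:

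- **SAP 4.4.2, PFS and DOR:** patients without progression or death before new therapy "will be censored at the last evaluable tumor assessment prior to or on the date of new anti-cancer therapy".
- **SAP 4.4.2, OS sensitivity analysis:** patients are censored when new therapy starts.
- **SAP 4.5, on-treatment period:** it ends at the last dose plus 90 days "or 1 day prior to starting a new treatment for cervical cancer, whichever is first".

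None of these refers to 6.4 or says what to do when the date is missing or partial.

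**The concern.** Choosing the earliest possible start is the cautious way to separate prior from concomitant medication, because a doubtful drug is then counted as overlapping study treatment. For the third category the caution runs the wrong way. A therapy given because study treatment had failed is moved back to the start of that treatment and tabulated as concomitant, although Protocol 8.7.1 bars other anti-tumour agents during the study.

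Incomplete dates are foreseeable. After progression, Protocol 9.1.4 plans contact about every four months, possibly by phone.

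The second problem is a gap. PFS, DOR, the OS sensitivity analysis and the treatment-emergent window all need a new-therapy date, and the only start-date rule in the SAP is one that does not suit them. What happens to such a patient would be settled in programming, although SAP Section 1 says the plan exists to fix such choices before database lock.

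**Working it through.** No figure stated in the plan bears on this point, so there is none to reproduce. The check applies the rules literally.

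**Classification.** SAP 6.4 can be read with first study treatment as the earliest date allowed or as the latest. Both readings put a fully missing start at or before first dose. SAP 4.3 requires a start after study drug stopped, so the post-treatment category cannot be reached. A year-only date in the year of first dose gives the same result, if the unknown parts are set to their earliest values; the SAP does not spell this out. A month-only date goes wrong only if the therapy began in the same calendar month as the last dose, since otherwise the first of the month falls after it.

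**One hypothetical patient.** The dates are assumptions: first dose 10 January 2022 (day 1), PR on days 50 and 92, last dose on day 114 (3 May), PD on day 134, new therapy truly started on day 160 (18 June).

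Formulas:

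- On-treatment end = the earlier of last dose + 90 days (114 + 90 = day 204) and therapy start − 1 day.
- PFS = event on day 134 if the therapy date is after day 134; otherwise censored at the last evaluable scan on or before the therapy date.
- DOR, counted from first response = end day − 50 + 1.

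| Date known, and use made of it | Therapy date | Class | PFS | On-treatment days | OS sensitivity |
|---|---|---|---|---|---|
| Full date | 160 | post-treatment | event, 134 | 1 to 159 | censored 160 |
| Month only, 6.4 date reused | 143 (1 June) | post-treatment | event, 134 | 1 to 142 | censored 143 |
| Missing or year only, 6.4 date reused | 1 | concomitant | censored, 1 | none (ends day −1) | censored 1 |
| Missing, no date used in 4.4.2 and 4.5 | none | concomitant | event, 134 | 1 to 204 | not censored at therapy |

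In the third row there is no post-baseline scan on or before day 1. The censoring day is therefore taken from the SAP 4.4.2 provision for patients with no evaluable post-baseline scan. DOR goes from 134 − 50 + 1 = 85 days with an event to 1 − 50 + 1 = −48 days, which is impossible. The allowance in SAP 4.5.1 for treatment-related events in the posttreatment period does not rescue the safety data, because SAP 4.5 also ends that period at new cervical cancer treatment.

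In the fourth row the progression is kept, but the on-treatment period is 204 − 159 = 45 days too long.

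**Scale.** The documents give no count of incomplete dates. As an assumed range, 1, 3, 5 or 10 patients would be 1.0%, 2.9%, 4.8% or 9.5% of 105. DOR has the smaller base: SAP Table 1 considers 21 to 36 responders, so one responder is 1/36 = 2.8% to 1/21 = 4.8%.

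**The case against.** The strongest reply is that the serious consequences are not in the plan. SAP 6.4 restricts its date to classification, plans no other imputation by default, and keeps the derived day out of listings. SAP 4.4.2 and 4.5 never cite it. A reader might infer that the rule erases PFS and DOR events and empties the treatment-emergent window. The documents do not support that: it would take a reuse of the date that goes against the SAP's own default. A DOR of −48 days, or a dosed patient with no on-treatment period, would also probably be noticed in programming.

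This part of the reply stands. It does not remove the gap, because without a date the new-therapy censoring and the on-treatment cut-off cannot be applied either.

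A second reply is that misclassification alone does little harm. Important deviations are determined separately before database lock (SAP 5.5), so the likely effect is a miscount in a concomitant-medication table. That is fair, and it limits the weight of the point. The rule still fails one of its three stated purposes.

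**Conclusion.** The point holds in two parts. First, with a fully missing start date, or a year-only date in the year of first dose, SAP 6.4 always classes subsequent anti-cancer therapy as concomitant. This follows from the text; the year-only case also assumes that unknown parts take their earliest values. Second, the SAP has no rule for an incomplete new-therapy date in PFS and DOR censoring, the OS sensitivity analysis or the on-treatment period. If the 6.4 date were borrowed, documented progressions would be wrongly censored and the on-treatment period emptied.

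No bias in PFS or DOR can be claimed from the plan as written, and its size cannot be estimated because the number of affected patients is unknown. Month-only dates usually do no harm. The primary ORR is unaffected, since best overall response in SAP 4.4.1 has no cut at new therapy, and main OS does not use the date. This is a modest correction, worth making because it is cheap.

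**What to change.** In SAP 6.4, limit the earliest-date rule to separating prior from concomitant medication, and exempt therapy recorded on the CRF as subsequent anti-cancer therapy. For that therapy:

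- Set an incomplete start date to the later of the first day of the known month or year and the day after the last study dose, kept within the known period.
- Use progression as a further lower bound only where the record states that the therapy followed that progression. When the therapy date is itself missing, dates alone cannot show the order.
- Cite this date in SAP 4.4.2 and 4.5, and state that the 6.4 classification date is not used there.

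In the worked patient, a month-only date stays at day 143 and the day-134 event is kept. A fully missing date becomes day 115 (114 + 1), correctly post-treatment. If the record says that the therapy followed progression, it becomes day 135 (134 + 1) and the event is kept. Without that statement, PFS would still be censored at the day-92 scan, so sites should be asked for the sequence.

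The cost is a few SAP sentences and minor programming; SAP Section 1 allows revision before database lock. The downside is that some therapies will be dated somewhat early or late: slightly so within a known month, more so when only the year or nothing is known.

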The total duration of study from start of screening to final analysis of OS is expected to be approximately 36 months (approximately 12 months of accrual, approximately 12 months of treatment, and approximately 12 months of follow up).

Figure 2: Study Flow Diagram

¹ Withdrawal due to reasons as listed in Section 7.3 and Section 8.2.2.

End of treatment is defined as the end of study drug. Patients may discontinue study drug for progression of disease or for any reason listed in Section 7.3 and Section 8.2.2. Thirty days after the last dose of study drug, patients will have EOT visit. Ninety days after the last dose of study drug, patients will have the safety follow-up visit (Table 2).

A patient who progresses on treatment will have EOT visit and safety follow-up visit. End of study (EOS) disposition will be on or after the safety follow-up visit. They will then enter survival follow-up.

A patient who discontinues treatment for reasons other than progression, as listed in Section 7.3 and Section 8.2.2, will have EOT and safety follow-up visit. They will then have tumor assessments until progression or the start of another anticancer therapy. At progression or start of another anticancer therapy, patients will have EOS disposition and then enter survival follow-up.

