9. STUDY SCHEDULE OF EVENTS AND PROCEDURES

9.1. Schedule of Events

Study assessments and procedures are presented by study period and visit in [Table 2](#).

The allowable window for all visit days and assessments is ± 3 business days (excluding weekends and holidays), unless otherwise stated. All other "days" in the protocol refer to calendar days. For tumor assessments (CT or MRI), the window is ± 7 days from planned scan dates, unless otherwise stated.

Missed doses of cemiplimab or visits will not be made up. In the case of missed doses of cemiplimab, tumor assessments should still follow original schedule. If a patient is unable to undergo scans within the window due to logistical or medical reasons, tumor assessment will be obtained at the next available date.

Missed doses of ISA101b are detailed in Section [8.3.1.3.1](#).

In light of the public health emergency related to COVID-19, the continuity of clinical study conduct and oversight may require implementation of temporary or alternative mechanisms. Examples of such mechanisms may include, but are not limited to, any of the following: phone contact, virtual visits, telemedicine visits, online meetings, non-invasive remote monitoring devices, use of local clinic or laboratory locations, and home visits by skilled staff. Additionally, no waivers to deviate from protocol enrollment criteria due to COVID-19 will be granted. All temporary mechanisms utilized, and deviations from planned study procedures are to be documented as being related to COVID-19 and will remain in effect only for the duration of the public health emergency.

Table 2: Schedule of Events

Study Procedure	Screening Visit ¹	Cycle 1 ^{2,3}				Cycle 2 to 4 ^{2,3}			Cycles 5+ ^{2,3}				EOT Visit ^{4,5}	Safety Follow-up ^{4,5}	Tumor Assessment ⁵	Survival Follow-up ^{4,5}
	Day -28 to Day -1	Day 1	Day 8 ±3	Day 29 ±3	Day 50 ±3	Day 1 ±3	Day 22 ±3	Day 43 ±3	Day 1 ±3	Day 22 ±3	Day 43 ±3	Day 64 ±3	30 days after last dose ±7 days	90 days after last dose ±10 days	Every 4 months (±10 days)	Every 4 months (±10 days)
Inclusion/exclusion	X															
Informed consent ⁶	X															
Genomics substudy informed consent (optional)	X															
PBMC consent (optional)	X															
Future biomedical research consent (optional)	X															
Medical history and demographics	X															
Electrocardiogram ⁷	X												X	X		
Performance status	X												X	X		
Tumor tissue sample	X ⁶															
Treatment:																

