9.1.2. End of Treatment Visit

All patients will attend an end of treatment visit 30 days after their last dose of study drug.

Patients who are withdrawn from the study before the primary endpoint visit (cycle 4 day 43) will be asked to return to the clinic once for an end of treatment visit consisting of the assessments described in [Table 2](#).

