5.6.2. Exposure to Investigational Product

Exposure to ISA 101b and cemiplimab will be examined for each subject and the following variables will be calculated:

- The total number of study doses administered
- The total dosage of study drug administered
- Duration of treatment exposure (in weeks) calculated as the minimum of
 - $[\text{date of last dose} - \text{date of first dose} + 21 \text{ days}] / 7$
 - or
 - $[\text{date of clinical data cut-off or date of death} - \text{date of first dose} + 1] / 7$
- The number and percentage of subjects exposed to cemiplimab will be presented by specific time point of interest.
- The actual dose intensity ($\mu\text{g} / \text{week}$) = total dose received (μg) / duration of treatment exposure (week) for ISA 101b
The actual dose intensity (mg / week) = total dose received (mg) / duration of treatment exposure (week) for cemiplimab
- The relative dose intensity = actual dose intensity / planned dose intensity
 - Planned dose intensity ($\mu\text{g} / \text{week}$) = planned dose (μg) / 3 for ISA 101b
 - Planned dose intensity (mg / week) = planned dose (mg) / 3 for cemiplimab

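### Replacing a missing last-dose date with the last visit date overstates exposure and understates dose intensity for patients who have already left treatment

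*SAP*

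**What the plan says.** SAP 6.4, in the paragraph on the dates of first and last study treatment, provides that if the last-dose date is wholly missing or not known, "his/her last visit date will be substituted". The rule does not define the last visit, does not limit it to dosing visits, sets no upper bound and does not treat the two drugs separately.

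The protocol fixes the visits that follow the last dose. Section 9.1.2: "All patients will attend an end of treatment visit 30 days after their last dose of study drug". Section 6.1: "Ninety days after the last dose of study drug, patients will have the safety follow-up visit". The Schedule of Events gives the timing and windows as "30 days after last dose ±7 days" and "90 days after last dose ±10 days". Patients who stop without progression then have scans about every 4 months (protocol 6.1 and 9.1.4).

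The last-dose date is used in two places in the SAP:

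- **SAP 5.6.2.** "Duration of treatment exposure (in weeks) calculated as the minimum of" two quantities: last dose minus first dose plus 21 days, or data cut-off or death minus first dose plus 1 day, each divided by 7. Dose intensity for each drug has this duration as its denominator.
- **SAP 4.5.** The on-treatment period runs from the first dose "to the last dose of study drug plus 90 days", or to the day before new treatment for cervical cancer if that is earlier. It governs treatment-emergent adverse events (4.5.1), worst-grade laboratory tables (5.8.2) and ECG shift tables (5.8.4).

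**The concern.** An imputed last-dose date should lie near a day on which drug was given. For a patient who has left treatment and returned for follow-up, the protocol places every later visit after the last dose, most of them by a planned interval. The substituted date is therefore late by design, and the error does not average out across patients.

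A patient who received every planned dose on time could be reported with half the planned dose intensity or less, and with weeks of exposure that did not occur. Those values enter the exposure tables and can set their extremes.

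**Working it through.** The plan states no figure that depends on this rule, so there is nothing to reproduce. The check applies the SAP's formulas to the planned schedule, first with the true last-dose date and then with the substituted one.

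**Inputs**

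- Cemiplimab 350 mg on day 8 and every 21 days thereafter; ISA101b on days 1, 29 and 50 (protocol 6.1).
- End-of-treatment visit 30 days after the last dose (window 23 to 37); safety visit 90 days after it (window 80 to 100).
- Exposure, dose intensity and caps from SAP 5.6.2. Planned intensity is planned dose / 3 per week for both drugs.
- Assumptions: all doses on time, no cap binding, and the rule applied to each drug's own last-dose date.

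**Cemiplimab**

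For k on-schedule doses and a substituted date g days late:

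- exposure = (21(k − 1) + g + 21) / 7 = (21k + g) / 7 weeks
- relative dose intensity = [350k / exposure] / (350 / 3) = 21k / (21k + g)

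For k = 4 (days 8, 29, 50 and 71):

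- true date: (71 − 8 + 21) / 7 = 12.0 weeks; 84 / 84 = 100%
- end-of-treatment visit, day 101: (101 − 8 + 21) / 7 = 16.3 weeks; 84 / 114 = 73.7%
- safety visit, day 161: (161 − 8 + 21) / 7 = 24.9 weeks; 84 / 174 = 48.3%

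| Doses | True exposure (weeks) | True intensity | Intensity, +30 days | Intensity, +90 days |
|---|---|---|---|---|
| 2 | 6 | 100% | 58.3% | 31.8% |
| 4 | 12 | 100% | 73.7% | 48.3% |
| 8 | 24 | 100% | 84.8% | 65.1% |
| 16 | 48 | 100% | 91.8% | 78.9% |

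The excess exposure does not depend on the number of doses. It is 30 / 7 = 4.3 weeks (3.3 to 5.3 over the window) or 90 / 7 = 12.9 weeks (11.4 to 14.3).

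**ISA101b**

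- true date: (50 − 1 + 21) / 7 = 10.0 weeks; 3 doses × 3 / 10.0 = 90%. This is below 100% because the SAP divides the planned dose by 3 weeks although the first two doses are 28 days apart.
- visit 30 days after day 50: 14.3 weeks, 63.0%
- visit 90 days after day 50: 22.9 weeks, 39.4%
- patient who continues to 8 cemiplimab doses (last on day 155), safety visit on day 245: (245 − 1 + 21) / 7 = 37.9 weeks; 9 / 37.9 = 23.8%

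**On-treatment period**

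If the missing date is that of the last study drug given, the period ends 30 + 90 = 120 days (113 to 127) or 90 + 90 = 180 days (170 to 190) after the true last dose, instead of 90. In the four-dose example, with ISA101b started on day 1, it ends on day 161 + 90 = 251 rather than day 71 + 90 = 161. The whole period is 251 / 161 = 1.56 times its proper length.

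**Effect on study-level summaries**

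Take the upper assumption of 2 affected patients, both with the safety visit substituted. Mean exposure rises by 2 × 12.9 / 105 = 0.2 weeks. If both had four cemiplimab doses, mean relative dose intensity falls by 2 × (100 − 48.3) / 105 = 1.0 percentage point.

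**The case against.** **The rule will seldom be used.** It applies only when the date is wholly missing, and both drugs are given in clinic. This stands and is why the point is minor. At 0 patients there is no effect; at 2 the medians would hardly move.

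**The last visit may mean the last dosing visit.** The sentence directly follows one that takes the first-dose date from the CRF dosing module, and imputing late matches the same section's treatment of missing medication end dates. That intention is possible, but the words do not say it, and a programmer following them would take the latest visit of any kind. A late end date is also harmless when deciding whether a medication was concomitant; here it goes straight into a denominator.

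**The error is not universal.** A reader might infer that the rule is wrong every time it is used. The documents do not support that. It is exact when the last visit was the last dosing visit, for example in a patient lost to follow-up after a dose. The cut-off and death caps limit excess exposure, and new cervical cancer treatment ends the on-treatment period. That last limit does not apply to exposure duration.

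**Safety counts.** A reader might also infer that the adverse event window doubles and that event counts are inflated. Only the tail after the last dose can double when the safety visit is substituted; the period itself starts at the first dose. Counts should change little, because routine recording stops 90 days after the last dose (protocol 10.1.1, SAP 4.5.1) and later related events already count as treatment-emergent (SAP 4.5.1). What remains is the occasional unrelated event recorded after day 90, for example at a safety visit held up to 10 days late.

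**Conclusion.** The point holds as a minor error in a stated rule. For a patient who has left treatment and attended follow-up, SAP 6.4 overstates exposure by about 4.3 or 12.9 weeks, or by more if a later scan visit is taken, and understates dose intensity accordingly. The error is largest for short cemiplimab courses, and for ISA101b when cemiplimab continues for months after day 50. The figures assume on-time dosing and no binding cap.

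It does not show inflated adverse event counts, and it does not touch ORR, PFS or OS, which SAP 4.4.1 and 4.4.2 define without the last-dose date. The number of affected patients, 0 to 2 of 105, is an assumption, since the documents give no rate. At that level the harm is to individual listed values and to the minimum and maximum in the exposure tables, not to the study's conclusions.

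**What to change.** Replace the sentence in SAP 6.4 with a rule applied separately to cemiplimab and ISA101b:

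- substitute the date of the latest dated administration record or, if a dose is recorded without a date, the date of the visit at which it was given;
- bound the result by the treatment discontinuation date, data cut-off and death;
- do not use end-of-treatment, safety, tumor-assessment or survival follow-up visits;
- list the patients for whom a date was substituted.

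The cost is a short SAP revision before database lock, which SAP 1 allows, and a little programming. The fix assumes that dosing-visit dates are held in the CRF, which was not available to check. It can err the other way if a whole dosing record is absent: each missing final cemiplimab record would shorten exposure by 21 / 7 = 3 weeks. That is smaller than the 4.3 or 12.9 weeks the present rule can add.
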